6 METHODS OF ASSESSMENT

Demographic Data

At Visit 9 (Day 0), subject demographic data will be collected. These include: year of birth, age, gender and race.

Medical History

At Visit 9 (Day 0) a complete medical history, including prior interventions to the study knee, will be obtained from each subject.

Concomitant Medications

Detailed history of medications will be documented for each subject at Visit 9 (Day 0). Concomitant medications (especially any changes in medication) will be documented for each subject at each scheduled visit.

Physical Examination and Vital signs

Height in feet and inches will be measured at Visit 9 (Day 0).

Body weight in pounds (lb) will be measured at Visit 9 (Day 0).

Body temperature (deg. F) will be measured at each visit.

Systolic and diastolic BP and pulse rate will be measured with the subject in a seated position.

The full physical examination will consist of examining the following body systems: cardiovascular, respiratory, abdominal, skin and musculoskeletal other than the knee. The physical examination of the study knee will consist of evaluating the knee joint for effusion and tenderness on palpation.

Kellgren-Lawrence Grading Scale

Radiographic images are evaluated according to the Kellgren-Lawrence Grading Scale as noted below in [Figure 2](#), as assessed in the Main Study

FIGURE 2: Kellgren-Lawrence Grading System

| Grade | Description |
|-------|--|
| 0 | Normal knee without osteophytes or joint space narrowing |
| 1 | Possible osteophytic lipping and doubtful narrowing of joint space |

| | |
|---|---|
| 2 | Definite osteophytes and possible narrowing of joint space |
| 3 | Moderate multiple osteophytes, definite narrowing of joint space and some sclerosis and possible deformity of bone ends |
| 4 | Large osteophytes, marked narrowing of joint space, severe sclerosis and definite deformity of bone ends |

6.1 EFFICACY ASSESSMENTS

Note: Efficacy questionnaire questions will be asked “with reference to study knee” i.e. to obtain scores specific for the treated knee.

6.1.1 WOMAC® Osteoarthritis Index ([Bellamy 1988](#))

WOMAC Index 3.1 should be completed by subjects at each in-clinic visit, pre-dose. All subjects are required to take at least 5 minutes to complete the questionnaire.

Subjects are asked about their pain, stiffness, and function in the study knee (study joint) due to arthritis during the last 24 hours. This will be assessed at every in-office visit.

Subjects will also be asked about their pain, stiffness, and function in the non-study knee. This will be assessed at Enrollment and Visit 17 (or early termination visit).

Subjects respond to each subscale by using a 5-point adjectival Likert score (0 = none, 1 = mild, 2 = moderate, 3 = severe, 4 = extreme).

6.1.2 Patient's Global Assessment of Disease Severity (PGA)

The PGA should be completed by subjects at each in-clinic visit (prior to injection).

Subjects are asked the following question: “Considering all the ways in which your arthritis affects you, please indicate how you are doing.”

Subjects respond by using a 5-point adjectival Likert score (0 = very well, 1 = well, 2 = fair, 3 = poor, 4 = very poor).

6.2 SAFETY PARAMETERS

Based on results of previous studies of a single intra-articular injection of Ampion™ < 5 kDa ultrafiltrate of 5% HSA in adults with OA of the knee in which no clinically significant differences between active and placebo were found, safety will be assessed by recording adverse events, vital signs, results of physical examination, by recording prior and concomitant medications, and safety labs (at the Visit 17/Early Termination visit only).

6.2.1 Vital Signs

Vital signs (radial pulse rate, blood pressure, and body temperature) should be recorded at each in-clinic visit, both pre-and post-dose (as applicable).

Vital signs should be taken after the subject has rested in a seated position for at least 5 minutes.

6.2.2 Clinical laboratory tests

Subjects will have lab tests at Visit 17 (or Early Termination) to evaluate for changes from Screening (Visit 1) of the Main Study.

The following analysis will be conducted:

Serum biochemistry: Sodium, potassium, chloride, bicarbonate, glucose, urea, creatinine, creatine kinase, urate, phosphate, total calcium, cholesterol, albumin, globulins, protein, total bilirubin, conjugated bilirubin, gamma glutamyltransferase (GGT), alkaline phosphatase (ALP), alanine aminotransferase (ALT), aspartate aminotransferase (AST) and lactate dehydrogenase (LD).

Hematology: Hemoglobin, red blood cell count, hematocrit, mean cell volume (MCV), mean cell hemoglobin (MCH), mean cell hemoglobin concentration (MCHC), platelets, white cell count, neutrophils, lymphocytes, monocytes, eosinophils, and basophils.

TABLE 6.1 SCHEDULE OF ASSESSMENTS AND PROCEDURES

| | Enrollment ¹ | Post-treatment phone contact | Week 12 | Post-treatment phone contact | Week 24 | Post-treatment phone contact | Week 36 | Post-treatment phone contact | Week 40 Final Visit | Early Termination |
|---------------------------------------|-------------------------------------|----------------------------------|------------------------|-----------------------------------|-------------------------|-----------------------------------|-------------------------|-----------------------------------|-------------------------|-------------------------|
| Visit # Day # | 9 ¹ Day -170 to Day 0 | 10 24 hours following Visit 9 | 11 Day 84 ± 14 days | 12 24 hours following Visit 11 | 13 Day 168 ± 14 days | 14 24 hours following Visit 13 | 15 Day 252 ± 14 days | 16 24 hours following Visit 15 | 17 Day 280 ± 14 days | 18 Early Termination |
| Informed Consent | X | | | | | | | | | |
| Inclusion/exclusion criteria | X | | | | | | | | | |
| Medical history/prior medications | X | | | | | | | | | |
| Concomitant medications | X | X | X | X | X | X | X | X | X | |
| Physical examination | X | | X | | X | | X | | X | X |
| Vital Signs | X | | X | | X | | X | | X | X |
| WOMAC ² | X ² | | X | | X | | X | | X ² | X ² |
| Subject's global assessment (PGA) | X | | X | | X | | X | | X | X |
| X-ray | X ³ | | | | | | | | X | X ⁸ |
| Clinical laboratory tests | | | | | | | | | X | X |
| Urine Analysis ⁴ | X ⁴ | | | | | | | | | |
| Treatment with study drug | X | | X | | X | | X | | | |
| Rescue medication ⁵ | X ⁵ | | X | | X | | X | | X | X |
| Review Rescue medication ⁶ | X ⁶ | X | X | X | X | X | X | X | X | X |
| Adverse Events ⁷ | X | X | X | X | X | X | X | X | X | X |

1. Subjects have 170 days to roll over from the AP-003-C main study (Visit 7) to this AP-003-C-OLE study (Visit 9). The first injection of the AP-003-C-OLE study is considered "Day 0". Visit 8 is accounted for in the AP-003-C main study in the event of Early Termination.
2. WOMAC also assessed for contralateral knee at Visit 9 and Visit 17 (or Early Termination visit, if applicable).
3. X-ray as assessed during Screening of AP-003-C main study.

4. For women of child-bearing potential, a HCG urine analysis must be completed at Visit 9 prior to enrollment in AP-003-C-OLE study to verify subject is not pregnant.
5. Rescue medication provided at Visit 9 and then as needed throughout the study. Bottles must be collected prior to dispensing a new bottle and at termination of AP-003-C-OLE study.
6. Use of rescue medication should be reviewed during each visit.
7. AEs at Visit 9 should be evaluated for ongoing AEs from the AP-003-C main study (pre-injection) and AEs occurring after injection.
8. X-ray to be obtained at Visit 18 unless subject terminates in order to get TKR. X-ray is unnecessary in this case.

7 DISCONTINUATION CRITERIA

7.1 EARLY DISCONTINUATION OF THE STUDY

It is agreed that for reasonable cause, either the investigator or the Sponsor may terminate this study, provided a written notice is submitted at a reasonable time in advance of intended termination; if by the investigator notice is to be submitted to Ampio Pharmaceuticals, Inc., and if by the Sponsor, notice will be provided to each investigator.

If a severe local reaction or drug-related SAE occurs at any time during the study, the Safety Monitoring Committee will review the case immediately.

The study will be immediately suspended and no additional Ampion™ treatments administered pending review and discussion of all appropriate study data by the SMC if 1 or more subjects develop any of the following adverse events deemed to be possibly, probably, or definitely related to Ampion™ by the Investigator and/or Medical Monitor, based upon close temporal relationship or other factors:

- Death
- Anaphylaxis (angioedema, hypotension, shock, bronchospasm, hypoxia, or respiratory distress)
- Induction of autoimmune arthritis
- Hepatic failure
- Aplastic anemia.

The study will not be restarted until all parties have agreed to the course of action to be taken and the IRB/EC has been notified.

7.2 EARLY DISCONTINUATION OF INDIVIDUAL SUBJECTS

Subjects are to be withdrawn from the study for any of the following reasons:

- Withdrawal of informed consent
- Subject is lost to follow up.

Subjects will also be withdrawn at any time if the investigator concludes that it would be in the subject's best interest for any reason. Protocol violations do not lead to subject withdrawal unless they constitute a significant risk to the subject's safety.

Subjects can voluntarily withdraw from the trial for any reason at any time. Sites should record the specific reason for withdrawing. Subjects are to be considered withdrawn if they state an intention to withdraw, fail to return for visits, or become lost to follow up for any reason. Subjects withdrawing from the study because of an AE should be followed for at least 30 days, resolution of the AE or until no further improvement is expected, whichever comes first.

8 TREATMENT

Eligible subjects will receive a single intra-articular injection every 12 weeks into one knee of Ampion™ at a volume of 4ml.

8.1 DOSING AND ADMINISTRATION OF STUDY MEDICATION

Appropriately trained site personnel should administer the study treatment.

It is required that the same study knee assessed in the AP-003-C main study be the same study knee in the AP-003-C-OLE study. At the time of dose administration, the study knee should be treated with received investigational product. The other knee should receive standard of care.

It is recommended that the study treatment be administered as an injection into the knee joint space under sterile prep conditions, (i.e. prior to injection, the knee should be cleaned with an antiseptic) to a subject who is in the seated position with the treatment knee flexed at 90°. The area of injection is inferior lateral to the patella; lateral level of the joint line. The Principal Investigator may determine whether anesthesia of the treatment area with a topical anesthesia, sub-dermal anesthesia, or nothing is appropriate. Intra-articular injection of lidocaine or other numbing agents are not allowed.

The recommended needle of choice for this injection is a 25-gauge needle that is 1.5 inches long. The needle may be passed through the fat pad to the firm surface of the intercondylar notch. Following the withdrawal of the needle, it is recommended that fingertip pressure be applied to the injection site, and then a sterile dressing (band aid) is used to cover the injection site. Injection should proceed easily. Failure to easily inject should be documented as a potential non-inter-articular injection.

The date of administration should be recorded in the study source notes/eCRF.

Subjects should be advised to abstain from submersing their knee in water for at least 24 hours (swimming pool, baths, lakes, etc.). Showering is acceptable.

8.2 DRUG STORAGE AND ACCOUNTABILITY

Study drug should be stored at room temperature (59° – 77°F or 15° – 25°C) in a secure area with restricted access. Temperature monitors, and instructions to download the temperature data to Ampio Pharmaceuticals, Inc., will be included with each site shipment of study drug.

The Investigator, the clinical site pharmacist, or other personnel authorized to store and dispense investigational product is responsible for ensuring that the investigational product used in the clinical study is securely maintained as specified by the Sponsor and in accordance with the applicable regulatory requirements.

All investigational product is to be dispensed in accordance with the Investigator's prescription and it is the Investigator's responsibility to ensure that an accurate record is maintained of investigational product issued and returned.

If any quality issue is noticed upon the receipt or use of an investigational product (i.e. deficiencies in condition, packaging, appearance, associated documentation, labeling, expiry date, temperature, etc.), Ampio Pharmaceuticals, Inc. must be promptly notified.

Under no circumstances may the Investigator supply investigational product to a third party, allow the investigational product to be used other than as directed by this clinical study protocol, or dispose of investigational product in any other manner.

All investigational product, used or unused during the study, must be retained in the study kit until notification from Ampio, or designated representative. Ampio, or designated representative, will instruct sites on study drug returns and/or destruction of study drug.

8.3 TREATMENT COMPLIANCE

The injection of study drug will be performed by the Investigator or a designated member of the site clinical staff. A 5mL syringe, 25-gauge needle, and a bottle of rescue medication will be included in every subject kit.

During monitoring visits, monitors will visually inspect each vial to ensure the full 4.0 mL injection volume was administered. Compliance with treatment is thus assured.

9 ADVERSE EVENTS

9.1 DEFINITION OF AN ADVERSE EVENT

An adverse event (AE) is defined as any undesired medical occurrence in a subject or clinical investigation subject receiving a pharmaceutical product and which does not necessarily have a causal relationship with this treatment. An AE can therefore be any unfavorable sign and unintended sign (including an abnormal laboratory finding), symptom, or disease temporarily associated with the use of a study drug, whether or not related to the study drug.

Assessment of severity of an AE will be rated according to categories listed in TABLE 9.1.

TABLE 9.1 DEFINITIONS OF AE SEVERITY

| |
|--|
| Grade 1 (MILD): The symptom is barely noticeable to the study subject and does not influence performance or functioning. Concomitant medication is not ordinarily indicated for relief of mild AEs. |
| Grade 2 (MODERATE): The symptom is of sufficient severity to make the study subject uncomfortable and to influence performance of daily activities. Concomitant medication may be indicated for relief of moderate AEs. |
| Grade 3 (SEVERE): The symptom causes severe discomfort, sometimes of such severity that the study subject cannot continue in the study. Daily activities are significantly impaired or prevented by the symptom. Concomitant medication may be indicated for relief of severe AEs. |

Determination of the relationship between the AE and the study drug will be made using the guidelines presented in TABLE 9.2.

**TABLE 9.2 GUIDELINES FOR DETERMINING THE RELATIONSHIP (IF ANY)
BETWEEN ADVERSE EVENT AND THE STUDY DRUG**

| | |
|-------------------------|---|
| Unrelated | The adverse event is unlikely to have been caused by study drug. |
| Possibly related | It is unclear whether the adverse event may have been caused by study drug. |
| Related | The adverse event is likely to have been caused by study drug. |

9.2 DEFINITION OF A SERIOUS ADVERSE EVENT

A Serious Adverse Event (SAE) is any untoward medical occurrence that occurs at any dose that:

- Results in death
- Is life-threatening (subject is at immediate risk of death from the event as it occurred)
- Requires in-subject hospitalization (formal admission to a hospital for medical reasons) or prolongation of existing hospitalization
- Results in persistent or significant disability/incapacity
- Results in a congenital anomaly/birth defect

Important medical events that may not result in death, are not life-threatening, or do not require hospitalization may be considered SAEs when, based on appropriate medical judgment, they may jeopardize the subject and may require medical or surgical intervention to prevent one of the outcomes listed in this definition. Examples of such events include allergic bronchospasm requiring intensive treatment in an emergency room or at home, blood dyscrasias or convulsions that do not result in in-subject hospitalization, or the development of drug dependency or drug abuse.

Hospitalizations for elective surgery or other medical procedures that are not related to a treatment-emergent AE are not considered SAEs.

9.3 RECORDING OF ADVERSE EVENTS AND SERIOUS ADVERSE EVENTS

Recording and reporting of adverse events should be in accordance with the FDA final “Guidance for Industry and Investigators Safety Reporting Requirements for INDs and BA/BE Studies” of December 2012.

Any AE is to be recorded in the eCRF. In order to avoid vague, ambiguous, or colloquial expressions, the AE should be recorded in standard medical terminology rather than the subject’s own words. Whenever possible, the investigator should combine signs and symptoms that constitute a single diagnosis.

The existence of an AE may be concluded from a spontaneous report of the subject; from the physical examination; or from special tests e.g., laboratory assessments, where applicable, or other study-specified tests (source of AE).

The reporting period begins from the time that the subject receives their first IA injection at the Baseline visit of the AP-003-C main study through subject’s Final Visit 17 at 40 weeks of AP-003-C-OLE study. Any events continuing at study exit will be followed for 30 days or to resolution, or until no improvement is expected, whichever comes first. Any SAE occurring after the reporting period must be promptly reported if a causal relationship to the investigational drug is suspected. If the subject begins a new therapy, the safety reporting period ends at the time the new treatment is started, however, death must always be reported when it occurs during the study period irrespective of intervening treatment.

Each AE is to be evaluated for duration, severity, seriousness, and causal relationship to the investigational drug. The action taken and the outcome must also be recorded.

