5.1.13 CONCOMITANT MEDICATIONS

The following medications / therapies are NOT allowed during this clinical study:

1. No IA injected pain medications in the study knee during the study. HA and steroid injections in the contralateral knee are acceptable while on study except \pm 14 days of Ampion injection in the study knee.
2. No analgesics containing opioids.
3. NSAIDS may not be used \pm 72 hours before/after IA injection of Ampion (in-office visits). Low-dose Aspirin (81 mg) is allowed but should not be used at least 24 hours prior to an in-office visit. Acetaminophen is available as a rescue medication during the study from the provided supply.
4. No non-pharmacological treatment targeting OA started or changed during the study.
5. No topical treatment on osteoarthritis study knee during the study.
6. No significant anticoagulant therapy (e.g. Heparin or Lovenox) during the study (treatment such as Aspirin or Plavix is allowed).
7. No systemic treatments that may interfere with safety or efficacy assessments during the study.
8. No immunosuppressants.
9. No use of systemic or intra-articular corticosteroids.
10. No human albumin treatment during the study.

Any medication used during the study should be recorded. All concomitant medication start and stop dates, total daily dose, route, and indication should be recorded.

The provided rescue medication during the 40-week extension study is 500 mg of acetaminophen, 1 tablet every 4 hours as required by the subject, not to exceed 3,000 mg of acetaminophen in a 24-hour period. Dose must be reduced if using other medications that contain acetaminophen (cold medicines, etc.).

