9.3.1 AE Follow up

All AEs occurring during the study are to be followed up in accordance with good medical practice until they are resolved, stabilized or judged no longer clinically significant or, if a chronic condition, until fully characterized. Any AEs that are considered drug-related (possibly related, definitely related) must be followed for 30 days, or to resolution, or until no improvement is expected, whichever occurs first.

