10.3.11 Data presentation

10.3.11.1 Demographic and Baseline Characteristics:

Demographic (e.g., age, sex, race, ethnicity) and baseline characteristics (e.g., weight, height) summarized using descriptive statistics, overall and by treatment group for the ITT analysis population.

10.3.11.2 Medical History and Physical Examination:

The number and percent of subjects with past and current medical disorders at the time of enrollment will be presented overall and by treatment group for the ITT analysis population. Results of any abnormalities documented from the physical examination will be summarized overall and by treatment group for the safety and ITT analysis populations.

10.3.11.3 Concomitant Medications or Treatments:

The number and percent of subjects receiving concomitant medications or treatments prior to and during the study and at the final visit will be tabulated and presented overall and by treatment group for the ITT analysis population. Concomitant medications/treatments will be summarized using descriptive statistics and will be presented by type of drug (WHO DRUG classification) overall and by treatment group for the safety and ITT analysis populations.

10.3.11.4 Safety data:

Safety data will be evaluated by changes in vital sign measurements and the frequency and severity of AEs. Concomitant medication will be recorded for safety.

Adverse events:

The Investigator is responsible for monitoring the safety of subjects who have enrolled in the study. All AEs considered to be possibly related to Ampion™ will be followed until the event resolves or stabilized without further change. Subjects will be followed for the occurrence of AEs until completion of the study at Visit 17 or until early termination from the study (if applicable).

Investigators are required to document all AEs occurring during the clinical trial, commencing with the first day of treatment and including the protocol-defined post-treatment follow-up period on the appropriate CRF pages.

The severity of AEs (mild, moderate, severe), relatedness (related, possibly related, unrelated) along with the duration, action taken, and outcome (e.g., study withdrawal) will also be recorded. In addition, events meeting the criteria of a Serious Adverse Event (SAE) must be reported to the Sponsor within 24 hours on the SAE reporting forms.

10.3.11.5 Efficacy data:

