10.4 STUDY ENDPOINTS

10.4.1 Primary Endpoint

- Incidence and severity of treatment-emergent adverse events (TEAEs).

These incidents will be summarized by number and percent of subjects having an event, the number of events per subject, and frequency of events in study population.

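### Protocol 9.3 ends AE reporting when an undefined new therapy starts, in conflict with follow-up to Visit 17, and can only lower the crude TEAE summaries

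*Protocol*

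**What the plan says.** Protocol 9.3 sets the AE reporting period from the first injection of the main study to "Final Visit 17 at 40 weeks of AP-003-C-OLE study". The same paragraph then states: "If the subject begins a new therapy, the safety reporting period ends at the time the new treatment is started". Two things survive that cut-off. One is death: "death must always be reported when it occurs during the study period irrespective of intervening treatment". The other is suspected drug-related SAEs: "Any SAE occurring after the reporting period must be promptly reported if a causal relationship to the investigational drug is suspected". Nothing says whether a new therapy means a drug or a procedure, for the study knee or any indication, on study or after exit.

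Other places give a different window:

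- Protocol 9.3.1: "All AEs occurring during the study are to be followed up in accordance with good medical practice".
- Protocol 10.3.11.4: "Subjects will be followed for the occurrence of AEs until completion of the study at Visit 17 or until early termination from the study".
- Protocol Table 6.1 and the schedule in SAP Section 10 mark AE collection at every visit, including early termination.
- SAP 4.7.4 stops AE follow-up twelve weeks after first dosing, yet its next paragraph has AEs documented to the end of the study.

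Other treatment can begin without the subject leaving. Protocol 5.1.13 says "HA and steroid injections in the contralateral knee are acceptable while on study", outside a window around each Ampion injection. Protocol 7.2 keeps subjects with protocol violations on study unless safety is significantly at risk.

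The primary endpoint is TEAE incidence and severity (Protocol 10.4.1). It is summarised by subjects with an event, events per subject and event frequency, and SAP 4.1 adds exact binomial 95% intervals for incidence.

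**The concern.** Long-term safety is the purpose of this study, and TEAEs are its primary endpoint. A site that follows 9.3 and a site that follows 10.3.11.4 would collect different data for that endpoint, and events never collected cannot reliably be recovered at analysis. No section censors follow-up at a new therapy, uses person-time, or says how events after a new therapy enter the tables. A subject whose reporting stops early therefore stays in the denominator as if fully observed.

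**Working it through.** **The texts side by side**

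| Source | AE collection ends at | New-therapy exception |
|---|---|---|
| Protocol 9.3, general rule | Visit 17 | see next row |
| Protocol 9.3, later sentence | start of a new therapy | deaths and suspected-related SAEs still reported |
| Protocol 9.3.1 | covers all AEs during the study | none |
| Protocol 10.3.11.4 | Visit 17 or early termination | none |
| Protocol Table 6.1 | every visit, including early termination | none |
| SAP 4.7.4, first statement | 12 weeks after first dose | none |
| SAP 4.7.4, second statement | end of study | none |
| SAP 5.2, TEAE definition | no end stated | none |

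**What is lost if 9.3 is followed.** After the new therapy starts, non-serious TEAEs and SAEs not suspected to be related go unreported. Protocol 10.5 puts all collected data into the safety assessment, but these would not be collected.

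**Direction.** With the denominator fixed at the full safety population, removing observation time can only leave the counts and percentages unchanged or reduce them.

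**Where the loss falls.** An AE that prompts a new therapy begins before it, so that subject already counts once for incidence. For such subjects the loss is in event counts and in later or more severe events. Incidence itself falls only through subjects with no AE before the new therapy.

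**Size, as illustration only.** The plan states no figure for this, so there is none to reproduce. Assumptions: a 40-week TEAE incidence of 45%; constant hazard; a share f of subjects starting a new therapy at a time uniform over 280 days and unrelated to earlier AEs; and the same hazard in everyone.

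- λ = −ln(1 − 0.45)/280, so 280λ = 0.5978.
- Mean observed incidence in starters = 1 − (1 − e^(−280λ))/(280λ) = 1 − 0.45/0.5978 = 0.2473.
- Observed incidence = (1 − f) × 0.45 + f × 0.2473.

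| f | Person-time lost (f/2) | Observed incidence | Points lost |
|---|---|---|---|
| 10% | 5% | 43.0% | 2.0 |
| 20% | 10% | 40.9% | 4.1 |
| 30% | 15% | 38.9% | 6.1 |

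**Sensitivity to the hazard in starters.** If starters have twice the hazard and the others stay at 45%, the loss is 2.8, 5.6 or 8.4 points.

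**Sensitivity to the base rate.** The documents give no 40-week rate. Protocol Table 1.5.4 has 145/326 = 44.5% of KL 4 Ampion subjects with a TEAE, pooled over earlier studies with primary endpoints mainly at Week 12 or 20. If that rate accrued over 12 weeks, the hazard is −ln(1 − 145/326)/12 = 0.0490 per week and the 40-week incidence is 1 − e^(−40 × 0.0490) = 85.9%. If it accrued over 20 weeks, the figures are 0.0294 and 69.2%. At equal hazard the losses for f = 10%, 20% and 30% are then 3.0, 5.9 and 8.9 points (12 weeks), or 2.8, 5.6 and 8.4 points (20 weeks). Doubling the starters' hazard changes these to 2.3, 4.6 and 6.9, or to 2.9, 5.8 and 8.7. A higher risk in starters therefore does not always enlarge the loss in any-TEAE incidence.

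**The case against.** The strongest defence is that the sentence concerns subjects who leave the study for another treatment. It follows sentences about events at and after study exit, and 10.3.11.4 also stops at early termination, so for such subjects there is little or no conflict. This is a possible intention, but the text does not say it. The clause that keeps deaths reportable during the study period despite intervening treatment would be unnecessary if the rule acted only after exit.

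A second defence is that the gravest events are retained. That is right as far as it goes: a reader might take death to be the only exception, but suspected-related SAEs are exempt too. Protocol 9.4.1 also asks for all SAEs to be entered within 24 hours, though it sets no period of its own and so does not settle which rule governs.

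A third is that subjects who start a new therapy because of an AE are already cases. This stands, and it limits the effect on subject-level incidence. It does not protect event counts, later or worse events, or subjects who start a therapy without a recorded AE.

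A reader might also infer that a permitted contralateral injection ends AE reporting in a subject still being dosed. The undefined term does not exclude that reading, but no passage states it, and Protocol 8.1 treats care of the other knee as routine.

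**Conclusion.** Wrong as written. Protocol 9.3 conflicts with 9.3.1, 10.3.11.4 and the schedule over when AE collection ends, and the conflict bears directly on the primary endpoint. If 9.3 is followed literally, the effect on the crude TEAE summaries is downward.

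The size is not known. The documents give neither the share of subjects starting a new therapy, nor the timing, nor a 40-week TEAE rate. The loss of 2.0 to 6.1 points rests on an assumed 45% incidence and assumed shares of 10% to 30%, and should be read only as an order of magnitude.

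It is tempting to go further and say that the truncation is informative. That is an inference. Protocol Table 9.1 notes that medication may be indicated for moderate or severe AEs, which makes a link plausible, but nothing in the documents establishes it. The conflict between the passages does not depend on it.

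**What to change.** Replace the new-therapy sentence in Protocol 9.3 with a rule that all AEs and SAEs are collected to Visit 17 or early termination, whatever therapy is started. State that the primary tables use all TEAEs in that window. In the same change, correct the 12-week follow-up statement in SAP 4.7.4 so that one AE window applies in both documents.

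Medication start dates are already recorded under Protocol 5.1.13, so TEAEs before any new therapy can be shown as an optional sensitivity summary, with a flag in the AE dataset.

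The cost is a short protocol amendment, a matching SAP correction, and slightly more AE entry at visits that already take place.
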